5. STUDY DESIGN

We propose a randomized comparative effectiveness trial to study systematically current Vt ranges to determine optimal settings to improve outcomes. Study participants will be randomly assigned to high tidal volume (14-16 ml/kg pbw) or low tidal volume of 8 to 10 ml/kg pbw within 48 hrs of admission. Subjects will be stratified based vital capacity at admission (≥ 5.8 cc/kg pbw) to ensure equal allocation of those with the most severe respiratory impairment and unlikely to wean from the vent. In our experience, vital capacity ≥ 5.8 cc/kg pbw was associated with higher odds of weaning. We will screen and recruit an additional 15 people with acute SCI not dependent on mechanical ventilation at admission to serve as controls. We anticipate 3 years to complete study recruitment. A 1:1 allocation ratio will be applied to the mechanical ventilation groups. Participants, principal investigator, outcome assessors, and statistician will be blinded to tidal volume assignment.

6. METHODS AND ASSESSMENTS

Intervention: Lower Vt group will be kept 8- 10 ml/kg pbw with PEEP, and in the high Vt group, the participant will receive a tidal volume of 14-16 ml/kg pbw with PEEP. The PEEP will be adjusted based on atelectasis on X-ray findings and patient tolerance within 5-10 cm H₂O range. These thresholds are used based on our cohort study²⁶ and survey data, which suggest the current median minimum to maximum Vt range used in rehabilitation hospital setting ranges from 8-16 ml/kg pbw. Tidal volumes will be increased per our institutional protocol at a rate of 50-100 ml per day until the target range is achieved. All participants at admission will be switched to Assist Control (AC) Mode or synchronized intermittent mandatory ventilation which is the current standard of practice in our free-standing acute inpatient rehabilitation unit. We will monitor peak and plateau pressures. All study participants will receive standard respiratory care, including secretion management using sub-glottic suction, mechanical insufflator-exsufflator, albuterol-ipratropium nebulization as-needed medications for thick secretions (e.g., N-acetylcysteine, guaifenesin).

Ventilator weaning Protocol is managed by board-certified SCI medicine rehabilitation physicians in our institution. Internal Medicine physicians are consulted on all our mechanically ventilated patients, and pulmonologists are available for consultation as needed. The ventilator

weaning protocol begins once the patient is determined to be medically stable by the attending physician and satisfies the following institutional criteria: lung auscultation with clear or relatively clear breath sounds, vital capacity >10-12 ml/kg pbw measured by Wright's spirometer via mouth or tracheostomy, chest X-ray clear or stable, arterial blood gas analysis on room air within normal limits, no active infection, hemoglobin >10 gm/deciliter and should be tolerating tracheostomy cuff deflation. The institutional weaning protocol consists of 12-19 days of progressive ventilator-free spontaneous breathing. The weaning schedule is adjusted sometimes due to respiratory complications, anxiety, and inability to tolerate protocol.

Control group: Both controls and people in mechanical ventilation groups will receive standard comprehensive inpatient rehabilitation services, including physical therapy, occupational therapy, speech, and respiratory therapy if needed.

Outcomes: The **primary outcome is pneumonia episodes** with evidence of new or progressive and persistent infiltrate on chest radiograph plus 2 of the following abnormal white blood cell count, presence of fever or hyperthermia, purulent sputum, and deterioration in gas exchange.²¹ Any new pneumonia episodes which meet the above criteria and developed 48 hrs after achieving target Vt will be recorded. New pneumonia events can only be recorded after 14 days from the onset of the first event.

The **secondary outcomes** include feasibility outcomes. We will obtain the following data: a) **Recruitment rate:** the proportion of eligible people who provide consent (b) **Adherence rate:** the proportion of participants in each group who receive assigned intervention per protocol; (c) **Retention rate:** the proportion of participants in each group who complete all study procedures and d) **Missing data:** Percentage of missing data in each group. Based on only one RCT²⁵ performed in SCI comparing high vs. low Vt, we anticipate a total recruitment rate of 80% (i.e., that 80% of the eligible would consent for the study), and of those who are enrolled in the study, 80% adherence and retention rate will be observed. We anticipate <10% missing data.

Additional outcomes: This data will be collected from the time of admission to our rehabilitation hospital until discharge. a) b) **Other respiratory complications:** The following ventilator-associated events will be reported: transfer to acute care hospital due to respiratory complications, weaning failure, new pneumothorax, ARDS, pleural effusion, pulmonary embolism, atelectasis, and pulmonary edema, and c) total ventilator days, weaning days and hospital length of stay.

We will perform an analysis of MV-related lung injury biomarkers. Blood and tracheal aspirate samples will be collected at 3-time points; at baseline within 48 hrs of admission to AIR facility, 48- 72 hrs after achieving target Vt, and 3rd sample post- weaning or 2 weeks from target Vt. Samples will be processed and stored at -80 ° C until use in [name] laboratory located at the Medical School, University of Texas in Houston, TX. We will focus on IL-1, IL-6, IL-8, and TNF- α levels. For controls we will obtain blood samples within 48 hrs of admission and 2 weeks from baseline.

Additional data: Additional data collection will include age, sex, weight, height, date of injury, date of admission to AIR, time since injury, mechanism of injury, American Spinal Injury Association (ASIA) impairment scale (AIS), vital capacity at admission, maximum vital capacity achieved during AIR stay, ventilator settings including Vt, peak and plateau pressure, hospital length of stay and discharge location. We will also collect information on any other ongoing or new infectious events other than pneumonia.

Randomization: Each subject will be randomized to either a tidal volume of 8-10 ml/kg pbw or 14-16 ml/kg pbw within 48 hrs of admission after obtaining consent. A 1:1 allocation ratio will be applied with permuted block size to maintain blindness and balance. Subjects will be stratified based on C1-C3 AIS A to ensure equal allocation of those with the most severe respiratory impairment and unlikely to wean from the vent. In our experience, C1-C3, AIS A was associated with lower vital capacity at admission. The study research assistant will randomize subjects in the redcap database, and he/she will not be involved in data analysis.

Blinding: The principal investigator (PI), statistician, outcome assessors, and participants will be blinded to tidal volume assignment.

Study Visits and Procedures:

Screening: Patients will be screened at the time of admission to TIRR Memorial Hermann. Respiratory therapist and SCI attendings will notify PI or research assistant (RA) regarding admits of an SCI patient dependent on mechanical ventilation or cervical SCI patients who are not dependent on MV (controls). PI or RA will discuss eligibility with respiratory therapists or attending physicians. PI may review discharge summary from acute care hospital or history and physical performed at TIRR admission to determine eligibility. If a person doesn't meet eligibility criteria, we will not save any identified data other than deidentified information on the reason for screening failure.

The screening will require information on age, past medical and surgical history, the duration of SCI, etiology of SCI, the dependence on a ventilator, neurological level and current medications.

Consent: If a subject agrees to participate, then they will be given an IRB-approved consent form to review and sign. There will be separate consent forms for MV group and controls due to different risks and procedures involved for participation in respective group. Those with tetraplegia will unlikely have the ability to sign and we will have a third-party attest to the consent. Because of the study's time constraints, they will have 1 day to decide upon whether they will participate.

Study procedures for MV group:

Day 0-1: screen, approach for informed consent
Day 1-2: obtain consent and randomization
Day 1-2: Baseline blood and tracheal specimen for inflammatory marker analysis
Day 1-4: Titrate tidal volume to achieve respective targets in each group
Day 4-6: 2nd blood and tracheal specimen (within 48 hrs after achieving target Vt)
Days 14-18: 3rd sample (post-weaning or 2-week sample)
Day 0- Discharge: Adverse events monitoring and outcome data collection

Study procedures for control group:

Day 0-1: screen, approach for informed consent
Day 1-2: obtain consent
Day 1-2: Baseline blood specimen for inflammatory marker analysis
Days 14-18: 2nd sample (2-weeks from baseline)
Day 0- Discharge: Adverse events monitoring and outcome data collection

We will collect demographics, outcome data, and adverse events from electronic medical records during their stay at TIRR (day 0- discharge).

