Subject Replacement: Subjects who drop out will be replaced by screening the inpatient unit. Subjects that drop out will be followed for secondary outcomes collected via the EMR while they remain at TIRR.

4. TRIAL SCHEDULE:

Participants will be enrolled in the study upon consent within 48-72 hrs of admission to TIRR MHH or Craig Hospital, and participation will end on discharge from respective hospital. The trial will start upon IRB and respective hospital approval on July 1, 2021, and end on June 30, 2024.

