8. TREATMENT

The current clinical practice guidelines recommend a higher tidal volume starting at 15 ml.kg predicted body weight (pbw) and up to 25 ml/kg pbw. These guidelines were written based on a small retrospective study and biological plausibility. People with SCI suffer hypoventilation due to paralysis of the muscle of inspiration. However, current data in people with and without ARDs suggests that lower tidal volume lowers the risk of morbidity and mortality and improves respiratory outcomes. Cohort study performed at TIRR also suggests that lower tidal volumes may lower the risk of pneumonia.

Our cohort study and a recent survey of physicians managing mechanical ventilators for people with SCI suggest practice variation in ventilator settings used for people with SCI.

Data from our center and international survey:

Variation in ventilator settings used for patients with acute SCI in acute care hospital at the time of discharge to a rehabilitation facility (Unpublished data): We collected data on 91 patients who required mechanical ventilation at the time of admission to acute inpatient rehabilitation (AIR) facility from 2015-2019. We noted variation (Figure 1.) in ventilator modes and settings used at acute care hospitals at the time of discharge. Median (interquartile range) tidal volumes were 7.5 (6.7-8.5) ml/kg pbw on admission to AIR facility or at the time of transfer from acute care hospital. 84% of patients were receiving PEEP on admission. After admission to the AIR facility, all patients were weaned off PEEP within the next 1-2 days and switched to assist control mode. Patients' tidal volumes were gradually increased to prevent atelectasis per SCI clinical practice guidelines.⁴ As a result, the median (IQR) tidal volumes received in rehabilitation hospital were 14 (13-16) ml/kg pbw. Our data suggest that ventilator settings used in acute care hospital and rehabilitation vary.

[figure not shown]

Figure 1: Ventilator modes at the time of discharge from acute care hospital

Abbreviations: Assist control; **SIMV:** Synchronized intermittent mandatory ventilation; **PS:** pressure support; **CPAP:** Continuous positive airway

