AEs and Reportable Events will be recorded. AE will be recorded on the appropriate case report form (CRF) page from the time written informed consent is obtained until completion of the study or until resolution of the reportable event. Information to be collected includes the description of the AE, date and time of onset, severity, duration, causality, outcome, and relationship to the study procedure. If an AE is assessed by the I

UTHealth
Houston

IRB NUMBER: HSC-MS-21-0222
as not reasonably
IRB APPROVAL DATE: 02/23/2023

attributable to study intervention, its occurrence must also be recorded in the source documents and reported on the CRF.

Safety Monitoring Plan

The Data Safety Monitoring Plan (DSMP) for the research study includes statistical analysis on rates of morbidity of study participants compared to controls by the PI and the statistician at 50% recruitment stage. If preliminary results suggest the risk of pneumonia is <25% in one group compared to another group, we will stop the study.

We will follow standard clinical procedures in the event of a desaturation episode. The most common cause of desaturation is a mucus plug in people with spinal cord injury in the rehabilitation setting. We will first suction the patient. If a patient is still not improving with suctioning, we will adjust ventilator settings, including tidal volume, to address clinical needs. Given that we have a range of VT in each group, we will first adjust within that range if VT has to be adjusted. If a person requires further adjustment in VT, we will allow the changes in ventilator settings to meet the patient's needs. We will not remove any patient from the study. We will include this data for intent to treat analysis. However, this event will be considered a treatment failure, and data will be included to calculate feasibility metrics for a larger study.

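### Primary-outcome pneumonia counts only from 48 h after target Vt, which the high arm reaches later, and the risk ratio makes no allowance for unequal time at risk

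*Combined protocol and SAP*

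**What the plan says.** Section 6 (Outcomes) names pneumonia as the primary outcome and limits what counts: "Any new pneumonia episodes which meet the above criteria and developed 48 hrs after achieving target Vt will be recorded".

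Time to target follows from three statements:
- Section 6 (Intervention) sets targets of 8-10 ml/kg pbw (low) and 14-16 ml/kg pbw (high), and says: "Tidal volumes will be increased per our institutional protocol at a rate of 50-100 ml per day until the target range is achieved".
- Section 8 reports, for 91 patients at one centre, that median (interquartile range) "tidal volumes were 7.5 (6.7-8.5) ml/kg pbw on admission to AIR facility". No value is given for the second site.
- Section 6 (Study procedures for MV group) gives one window for both arms: "Day 1-4: Titrate tidal volume to achieve respective targets in each group".

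Under section 4, "participation will end on discharge from respective hospital". Section 11 (Aim 1) reports a risk ratio with a credible interval and a posterior probability, under a neutral prior centred at 1 with 95% interval 0.3 to 3. It mentions no offset, rate, time-to-event model or fixed window. It refers to matching frequentist models, but none is described for Aim 1.

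Data are gathered over the whole stay: "Day 0- Discharge: Adverse events monitoring and outcome data collection". Section 9 lists pneumonia among the adverse events. For patients whose Vt has to leave the assigned range, section 9 says: "We will include this data for intent to treat analysis". It also calls them treatment failures for the feasibility metrics.

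**The concern.** A typical patient arrives at or just below the low range and about 6.5 ml/kg below the high range. The low-arm clock can start almost at once, while the high-arm clock waits for titration. Nothing at the end of follow-up makes up the lost days. Pneumonia during that extra wait is recorded only as an adverse event and does not enter the primary comparison. The two arms are then compared over different parts of the stay.

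If hazard and length of stay are equal in the two arms, leaving out more high-arm time lowers the recorded high-arm risk and pushes the low/high ratio above 1. That works against Hypothesis 1, which looks for more than 70% posterior probability that the low arm has the lower risk.

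A second difficulty concerns patients who never reach target. Read literally, the definition gives them no counting window, although section 9 keeps patients who need Vt outside the range in the intent-to-treat analysis.

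The bias does not shrink as the sample grows. Section 1 says the pilot is meant to show that the methods will work in a large trial, so the rule could be carried forward.

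**Working it through.** **Inputs from the documents:** targets 8-10 and 14-16 ml/kg; 50-100 ml/day; admission Vt 7.5 (6.7-8.5) ml/kg; Day 1-4 window; 48 h lag; 15 per arm; prior 0.3 to 3; 70% threshold.

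**Assumed, because the documents do not give them:** predicted body weight (PBW) 50-80 kg, whole-stay risk 40%, constant hazard, stay of 42 or 60 days and equal in both arms.

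**1. Extra wait in the high arm.** For any admission Vt up to 8 ml/kg, the gap is (14 - 8) × PBW / daily step.
- 50 kg at 100 ml/day: 300/100 = 3.0 days.
- 70 kg: 420/100 = 4.2 to 420/50 = 8.4 days.
- 80 kg at 50 ml/day: 480/50 = 9.6 days.
- From the upper quartile of 8.5 ml/kg the low arm is already in range, and the gap is 5.5 × PBW / step = 2.75 to 8.8 days.

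**2. Does the Day 1-4 window fit?** Four steps from 7.5 ml/kg reach 14 ml/kg only if PBW is at most 400/6.5 = 61.5 kg (100 ml steps) or 200/6.5 = 30.8 kg (50 ml steps). The window therefore conflicts with the titration rate and admission Vt for most of the assumed body sizes. If it did hold, the largest gap pairs low-arm target on day 1 with high-arm target on day 4, which is 3 days.

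**3. Recorded ratio with no true effect.** Hazard h = -ln(0.6)/L, and recorded risk = 1 - exp(-h × (L - opening day)). The low-arm window opens on day 1 + 2 = 3. The high-arm window opens on day 6 (day schedule, largest gap), or on day 7, 9 or 11 (titration rate at 70 kg, gaps of about 4, 6 and 8 days).

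| High arm opens | Risk low v high, L = 42 | RR, L = 42 | Fewer high-arm events per 15 | RR, L = 60 |
|---|---|---|---|---|
| Day 6 | 0.378 v 0.355 | 1.07 | 0.35 | 1.04 |
| Day 7 | 0.378 v 0.347 | 1.09 | 0.47 | 1.06 |
| Day 9 | 0.378 v 0.331 | 1.14 | 0.71 | 1.09 |
| Day 11 | 0.378 v 0.314 | 1.20 | 0.95 | 1.13 |

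Of the 40% true risk at 42 days, the low arm loses 2.2 percentage points. The high arm loses 4.5 (day 6) or 5.3-8.6 (days 7-11). The standard error of log RR with 15 per arm is 0.48-0.51, so the shift in log RR (0.063-0.184) is 0.13-0.36 of one standard error.

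**4. Other hazard shapes and stays.** Take randomisation on day 2, one day to target in the low arm and 5, 7 or 10 days in the high arm. Constant hazard then gives 1.15-1.45 for a 30-day stay and 1.04-1.09 for 90 days. If the hazard is three times higher in the first 14 days, the ranges are 1.32-2.40 and 1.10-1.28.

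**5. Effect on Hypothesis 1.** The prior on log RR is normal with mean 0 and SD ln(3)/1.96 = 0.56. The likelihood for log RR is normal, with 0.5 added for zero cells, and the result is summed exactly over the two binomials. True whole-stay risks are assumed to be 28% v 40%. Chance that the posterior probability exceeds 70%:

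| Windows open (low v high) | 42 days | 60 days |
|---|---|---|
| Day 3 v 3 | 51% | 52% |
| Day 3 v 6 | 45% | 48% |
| Day 3 v 7, 9, 11 | 43%, 39%, 34% | 46%, 43%, 41% |

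These falls are somewhat overstated if high-arm patients carry low-arm risk until they reach target. In that case a common day-3 origin gives 50% (day schedule) or 50-47% (titration rate) at 42 days, and 51% or 51-49% at 60 days. Both remain above the current rule.

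**6. Never at target.** One such patient kept in a denominator of 15 lowers that arm's recorded risk by 1/15 = 6.7% in relative terms, in either arm. The documents give no rate.

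**The case against.** The best opposing case is about size, rationale and remedy.

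- **The day-schedule figure is a maximum.** It pairs the earliest low-arm day with the latest high-arm day. With low-arm target on day 2 and high-arm target on day 4, the windows open on days 4 and 6. The ratio is then 0.370/0.355 = 1.04 at 42 days and 0.379/0.369 = 1.03 at 60. This stands, and the 1.07 should be read as an upper bound.
- **Vt might rise before allocation.** Admission Vt comes from one centre, and randomisation may follow up to 48 h later. Any rise in between would shorten the gap. At the upper quartile of 8.5 ml/kg, four 100 ml steps reach 14 ml/kg up to 400/5.5 = 72.7 kg. This stands as a limit on size. Direction would change only if the arms reached target together, which the stated rate does not support for most of the assumed sizes.
- **Length of stay may differ by arm.** If later titration lengthened the high-arm stay by the same number of days, the constant-hazard ratio would return to 1.00. Nothing in the plan ensures this. A common origin followed to discharge has its own weakness: with no effect, stays of 42 v 49 days give 0.88, and the reverse gives 1.13. A person-time or fixed-horizon analysis is needed for this reason.
- **The lag has a purpose.** It keeps out pneumonia that began before the assigned exposure. That is reasonable, but a lag fixed from randomisation does much the same and treats the arms alike.
- **It is a feasibility pilot.** Section 11 gives feasibility as the purpose, no go/no-go rule uses the 70% figure, and the bias cannot manufacture a benefit for low Vt. All true, and the reason this is not a fatal fault. Pneumonia is still the named primary outcome, and Hypothesis 1 rests on it.

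**Conclusion.** The concern holds and should be fixed. The counting rule is explicit. The later high-arm start follows from the plan's own titration rate and admission Vt, and no adjustment for time at risk is stated. With equal hazards and stays, the recorded low/high ratio is biased upward, against Hypothesis 1.

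The size is modest and rests on assumed PBW, risk, stay and hazard shape. With a 40% risk and constant hazard it is up to 1.07 (42 days) or 1.04 (60 days) on the day schedule, and 1.09-1.20 or 1.06-1.13 at the titration rate and 70 kg. Short stays or early pneumonia make it larger. At 70 kg it is below one event per 15 and well inside sampling error, but it is systematic, so a larger trial using the same definition would inherit it. Confidence is high on the rule and its direction, and lower on any single figure.

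**What to change.** - **Primary count.** In section 6, count new pneumonia in every randomised ventilated patient, analysed as randomised, from one origin that does not depend on the arm: randomisation, or a fixed 48 h after it. Follow to discharge whether or not target Vt was reached. This also settles the never-at-target patient and agrees with the intent-to-treat statement in section 9.
- **Supporting analysis.** In section 11, add events per person-time or risk to a fixed day, because stay may differ by arm.
- **Sensitivity analysis.** Keep the current count from 48 h after target.
- **Reconcile the text.** The Day 1-4 window, the titration rate and the admission Vt must be made consistent. No view is taken here on which is right.

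The cost is one change of definition and two short analyses. Outcome data already run from day 0 to discharge, and section 6 already lists "total ventilator days, weaning days and hospital length of stay" among the outcomes. The adjudication panel would see a few more episodes among 30 patients. The drawback is that some events before full separation in Vt are counted, which slightly dilutes the contrast. The sensitivity analysis will show by how much.

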3. STUDY POPULATION

Sample Size: We plan to recruit 45 subjects (15 in low Vt, 15 in high Vt, and 15 in the control group). We will recruit 30 adults with acute cervical SCI admitted on mechanical ventilation from TIRR MHH and Craig Hospital and an additional 15 people with acute cervical SCI not dependent on mechanical ventilation at admission to serve as controls from TIRR MHH.

Criteria for Recruitment: All consecutive patients with SCI admitted to TIRR MHH and Craig Hospital will be screened for eligibility based on inclusion and exclusion criteria during the study period. The screening will involve the review of history from the patient or primary admitting clinician. If a patient meets eligibility criteria, the research coordinator will provide further information on the study, answer any questions, and recruit if they are willing to participate and provide consent.

Inclusion Criteria: Subjects must meet all of the inclusion criteria listed below to participate in this study.

- Adult patients \geq 18 years (Lung volumes and ventilator settings are different for ages <18 years).
- Acute SCI of duration \leq four months
- Mechanical ventilation subjects: traumatic or non-traumatic cervical SCI with neurological level C1-C5 admitted to our acute inpatient rehabilitation facility (AIR) on mechanical ventilation.
- Control subjects: traumatic cervical SCI admitted to our acute inpatient rehabilitation facility (AIR) who are not dependent on mechanical ventilation.

Exclusion Criteria: All subjects meeting any of the exclusion criteria listed below at baseline will be excluded from participation.

- Severe dysphagia due to concomitant brain stem injury, which increases the risk of pneumonia
- Severe brain injury resulting in dysphagia and inability to follow instructions to perform vital capacity measurements
- ARDS or severe lung disease (required supplemental oxygen or ventilator prior to SCI) at the time of admission (these conditions will not allow patients to randomize because target Vt may below)
- Prolonged antibiotics for > 3 weeks at the time of admission due to infection (e.g., osteomyelitis, epidural abscess, etc.),
- Presence of diaphragmatic pacemaker.

Withdrawal Criteria: Possible reasons for discontinuation of study intervention: Intolerance to proposed ventilator settings.

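### The window for the additional respiratory complications opens at admission, before randomisation, and no onset rule keeps pre-existing atelectasis, pleural effusion, pulmonary embolism or pulmonary oedema out of the between-arm comparison

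*Combined protocol and SAP*

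**What the plan says.** Section 6 (Methods and Assessments), under additional outcomes, sets the window: "This data will be collected from the time of admission to our rehabilitation hospital until discharge". The events to be reported are transfer to acute care for respiratory reasons and "weaning failure, new pneumothorax, ARDS, pleural effusion, pulmonary embolism, atelectasis, and pulmonary edema". The schedule for the ventilated group in the same section repeats the window: "Day 0- Discharge: Adverse events monitoring and outcome data collection".

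Allocation comes later. Patients are randomised "within 48 hrs of admission after obtaining consent", which the schedule places on Day 1-2, and the assigned change in ventilation follows: "Day 1-4: Titrate tidal volume to achieve respective targets in each group".

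The primary outcome is handled differently. Only new pneumonia episodes that "developed 48 hrs after achieving target Vt will be recorded" qualify.

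Section 3 (Study Population) excludes "ARDS or severe lung disease (required supplemental oxygen or ventilator prior to SCI) at the time of admission". It has no matching exclusion for atelectasis, effusion, embolism or oedema.

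Section 9 (Safety Measurements) lists the same complications as adverse events. It records them "from the time written informed consent is obtained until completion of the study", with date and time of onset among the items captured.

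Section 11 (Sample Size and Statistical Methods), Aim 1, reports respiratory outcomes as relative risks with credible intervals and posterior probabilities. It states no other counting window.

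**The concern.** A condition already present when a patient is randomised cannot be an effect of the assigned tidal volume. If it still counts as an outcome, both arms receive the same expected background and the contrast between them shrinks. In a small trial the background may also fall unevenly by chance and look like benefit or harm.

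Atelectasis makes this more than a formality. Sections 1 and 8 give its prevention as the reason for high tidal volumes in spinal cord injury, so a diluted comparison of atelectasis could mislead the design of the larger trial that this pilot is meant to inform. Section 6 also has PEEP adjusted for atelectasis seen on X-ray, so the finding is expected in these patients.

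The time order matters for Aim 3 too. Hypothesis 3.3 says that patients with higher marker levels are more likely to develop respiratory complications. A complication that was present before the baseline sample says nothing about that.

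**Working it through.** **Step 1: timeline.** The outcome window opens on Day 0, randomisation is on Day 1-2, and titration runs over Days 1-4. Up to 48 hours of the window therefore precede allocation under Section 6. Section 4 allows enrolment as late as 72 hours after admission. Section 9 starts the same events at consent, so the documents give two start times and neither is randomisation.

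**Step 2: which events are exposed.**

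| Event | Can a case present at admission enter? |
|---|---|
| Acute-care transfer, weaning failure | No: cannot already be present at admission |
| Pneumothorax | No: must be new |
| ARDS | No: excluded at admission |
| Atelectasis, pleural effusion, pulmonary embolism, pulmonary oedema | Yes: no onset rule and no exclusion |

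**Step 3: dilution.** The plan states no event rate, effect size or power for these outcomes, so there is no figure to reproduce. All risks below are assumptions. Let q be the prevalence at admission, equal in expectation across arms through randomisation, and r the risk of new onset after randomisation. If any occurrence from admission counts:

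observed risk = q + (1 − q) × r

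The risk difference is multiplied by (1 − q), and the relative risk (low/high Vt) moves towards 1.

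| q | Low, r = 0.20 | High, r = 0.40 | Relative risk |
|---|---|---|---|
| 0 | 0.20 | 0.40 | 0.50 |
| 0.20 | 0.20 + 0.80 × 0.20 = 0.36 | 0.20 + 0.80 × 0.40 = 0.52 | 0.69 |
| 0.40 | 0.40 + 0.60 × 0.20 = 0.52 | 0.40 + 0.60 × 0.40 = 0.64 | 0.81 |
| 0.60 | 0.60 + 0.40 × 0.20 = 0.68 | 0.60 + 0.40 × 0.40 = 0.76 | 0.89 |

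With assumed risks of 30% versus 60%, the relative risk of 0.50 becomes 0.58, 0.65, 0.71 and 0.76 at q = 10%, 20%, 30% and 40%. The dilution works in the other direction as well. If low Vt doubled the risk (40% versus 20%), the relative risk of 2.00 would become 0.52/0.36 = 1.44 at q = 20% and 0.64/0.52 = 1.23 at q = 40%.

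**Step 4: chance imbalance.** With 15 per arm, treat the number of prevalent cases in each arm as an independent binomial count (15, q). The probability that the arms differ by 3 or more is 12% at q = 10%, 25% at 20%, 32% at 30% and 35% at 40%. In a simulation with new-onset risks of 30% and 60%, adding prevalent cases moved the observed relative risk further from 1 in 20%, 17%, 14% and 11% of trials at the same four prevalences. The pull towards 1 is therefore an average and not a certainty in one trial.

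**The case against.** The strongest reply is that collecting is not counting. Section 6 says when data are gathered and which events are reported. It does not say that a finding on the admission film scores as an event. Gathering from admission is sensible, since the same sentence also covers ventilator days and length of stay, and the schedule serves the non-randomised controls too. Section 9 records the date and time of onset of each adverse event, so early events could be separated at analysis. Section 8 has a panel judge whether events meet diagnostic criteria. One could also read 'new' as governing everything listed after it.

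Much of this stands. A reader might infer that the protocol deliberately scores admission findings as events, and the text does not say so. What remains is that admission to discharge is the only window given for these outcomes, while the primary outcome in the same section has an explicit onset rule. The panel does not close the gap, because no criteria are written for events other than pneumonia. Adverse event recording starts at consent, so it does not by itself document what was present at admission. The broad reading of 'new' is possible but is not stated.

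It is also fair that these rank below the primary and feasibility outcomes in a pilot sized on feasibility.

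**Conclusion.** The point holds for four conditions: atelectasis, pleural effusion, pulmonary embolism and pulmonary oedema. Following the stated window would let cases that precede allocation enter the between-arm relative risks. On average this dilutes the effect: an assumed 0.50 becomes 0.69 at 20% prevalence and 0.81 at 40%. The true size cannot be computed, because the documents give no admission prevalence. The illustration assumes that prevalence is equal across arms in expectation and that each patient counts once per condition.

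Three stronger readings are tempting and not supported:

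- That all the listed complications are affected. Transfer, weaning failure, pneumothorax and ARDS are largely untouched (step 2).
- That the 74-84% in Section 1 measures prevalence at admission. It is a figure for the acute phase and includes pneumonia and ventilatory failure.
- That the trial's main result is compromised. The primary outcome has its own new-onset window, and the stopping criterion in Section 9 is worded on pneumonia.

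This should be corrected, but it is a fault in additional outcomes and no threat to the primary comparison.

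**What to change.** 1. **Section 6, additional outcomes and schedule.** Keep collecting from admission. For the randomised comparison, count atelectasis, pleural effusion, pulmonary embolism and pulmonary oedema only if onset, or clear worsening from the admission record, is after randomisation. Use the onset date already recorded under Section 9, and give the panel a written definition of clear worsening.
2. **Baseline reporting.** Tabulate cases of these conditions present before randomisation as baseline characteristics by arm.
3. **Controls and Aim 3.** Controls are not randomised, so use the baseline sample date as the start for them and for the biomarker analysis.
4. **Sections 6 and 9.** Reconcile the admission and consent start times, and state that the between-arm comparison of these events as adverse events starts at randomisation.

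Randomisation is a better start than reaching target Vt, because the time to target differs by arm. Section 8 gives a median of 7.5 ml/kg at admission and Section 6 a rate of 50-100 ml per day. At an assumed predicted body weight of 70 kg, reaching 14 ml/kg needs (14 − 7.5) × 70 = 455 ml, or 4.55 to 9.1 days. Reaching 8 ml/kg needs 0.5 × 70 = 35 ml, under one day.

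The cost is revised wording, one present-at-admission field taken from the medical record, and fewer counted events.
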